## **7.9 Other Assessments**

Assessments to be performed at Screening only are detailed in the Schedule of Assessments ([Section 1.3](#)).

## **8 PSYCHOMETRIC ASSESSMENTS**

Psychometric assessments will be administered in a neutral, non-leading manner to minimize the chance for bias. Avoiding a biased administration can be achieved by adhering to questionnaire administration guidelines verbatim and only deviating from the script to clarify, re-direct or query further if behavioral examples are needed to determine the appropriate symptom intensity rating.

All clinician-rated psychometric assessments will be administered by a central rater via telephone or video call. Remote assessments assure that the assessor who is collecting the primary outcome measures will not witness dose sessions and the acute effects of methylone, which strengthens the study blind. The central ratings will be recorded in order to ensure quality ratings and rater fidelity across the central rater pool.

Copies of each scale can be found in the Investigator Site File.

### **8.1 Clinician-Administered Psychometric Assessments**

#### **8.1.1 Clinician-Administered PTSD Scale for DSM-5 (CAPS-5)**

The CAPS-5 is a 30-item structured interview that can be used to:

- Make current diagnosis of PTSD.
- Assess change in PTSD symptoms over time.

In addition to assessing the 20 DSM-5 PTSD symptoms, questions target the onset and duration of symptoms, subjective distress, impact of symptoms on social and occupational functioning, improvement in symptoms since a previous CAPS administration, overall response validity, overall PTSD severity and specifications for the dissociative subtype (depersonalization and derealization). The CAPS-5 also rates intrusion symptoms (intrusive thoughts or memories), avoidance, cognitive and mood symptoms, arousal and reactivity symptoms, duration and degree of distress. For each symptom, standardized questions and probes will be provided.

The ‘past month’ version of the CAPS-5 will be performed at Screening. The ‘past week’ version of the CAPS-5 will be performed at each subsequent study visit. The participant will report on the same Criterion A event specified at Screening for all CAPS-5 assessment timepoints.

Each CAPS-5 will be administered by a central rater via telephone or video call.

#### **8.1.2 Mini International Neuropsychiatric Interview**

The MINI 7.0.2 is a short, structured diagnostic interview that is compatible with DSM-5 and International Classification of Disease criteria for psychiatric disorders. Each module of the MINI consists of two or three questions where the answer is either ‘Yes’ or ‘No’, and a decision-tree logic is used to determine whether to ask additional questions. The PTSD, suicidality, and antisocial personality disorder modules of the MINI are not required to be administered as these are addressed via other scales.

The MINI will be administered at Screening by a central rater.

#### **8.1.3 Structured Clinical Interview for DSM-5 Personality Disorders (SCID-5-PD)**

The SCID-5-PD is a structured diagnostic interview to assess for DSM-5 personality disorders.

In this study, participants who endorse a positive response for paranoid personality disorder, antisocial personality disorder, or borderline personality on the SPQ will be administered the SCID-5-PD for those personality disorders.

The SCID-5-PD, if needed, will be administered at Screening by a central rater.

#### **8.1.4 Structured Interview Guide for the Montgomery-Åsberg Depression Rating Scale (MADRS) (SIGMA)**

The SIGMA is a standardized version of the MADRS. The SIGMA maintains the original format of the MADRS, which is a 10-item clinician-rated, diagnostic questionnaire used to measure depression severity, with the exception that the first two items are reversed. Each item is measured on a 7-point scale, from 0 to 6. Higher total MADRS scores indicate more severe depression. Follow-up questions are also provided to clarify symptoms, if required.

The MADRS will be administered at by a central rater.

#### **8.1.5 Clinician Global Impressions Scale – Severity**

The CGI-S is designed to acquaint the participant’s severity of symptoms with those of other people experiencing the same mental ailment. The CGI-S rates this severity on a 7-point scale, with (1) representing normal symptoms, meaning the participant is not ill, and (7) representing participants among the most severely ill. The rating (4) represents a participant that is defined as a participant that is defined as moderately ill.

The CGI-S will be administered at by a central rater.

#### **8.1.6 Clinician Global Impressions Scale – Improvement**

The CGI-I is a 7-point scale that requires the assessor to assess how much the participant’s illness has improved or worsened relative to a baseline state prior to dosing. The CGI-I scale rates improvement with (1) representing a ‘very much improved’ participant to (7) representing a participant who has become ‘very much worse’ due to treatment. The rating (4) represents a participant displaying no change from the treatment.

The CGI-I will be administered at by a central rater.

### **8.2 Participant-Completed Psychometric Assessments**

#### **8.2.1 PTSD Checklist for DSM-5 (PCL-5)**

The PCL-5 is a 20 item self-report measure that assesses the presence and severity of the 20 DSM-5 symptoms of PTSD. The PCL-5 has a variety of purposes, including:

- Monitoring symptom changes during and after treatment.
- Screening individuals for PTSD.
- Making a provisional PTSD diagnosis.

Participants will be asked to rate each item from 0 (‘not at all’) to 4 (‘extremely’) to indicate the degree to which they have been affected by that particular symptom over the past week; the results will be interpreted by a clinician.

#### **8.2.2 Life Events Checklist for DSM-5 (Extended Version)**

The LEC-5 is a brief, 17-item self-report measure designed to screen for potentially traumatic events in a participant’s lifetime, to facilitate the diagnosis of PTSD. It is a companion to the PCL-5 and will be used to assess PTSD. The extended version of the LEC-5 should be used to establish the worst event if more than one event occurred.

### **8.2.3 Structured Clinical Interview for DSM-5 Screening Personality Questionnaire (SCID-5-SPQ)**

The SCID-5-SPQ is a self-report screening tool to assess for DSM-5 personality disorders.

Participants will be required to only complete questions specific for assessing personality disorders (paranoid personality disorder, antisocial personality disorder, or borderline personality). In this study, participants who endorse a positive response for paranoid personality disorder, antisocial personality disorder, or borderline personality on the SPQ will be administered the SCID-5-PD for those personality disorders.

### **8.2.4 Sheehan Disability Scale**

The SDS is a brief, 5-item self-report tool that assesses functional impairment in work, social life/leisure activities and family life/home responsibilities. The SDS is designed to measure the extent to which the three major domains in the participant's life are functionally impaired by psychiatric or medical symptoms. Each domain is rated from 0 to 10, with a total score from 0 to 30, where 0 – Unimpaired and 30 – Highly impaired.

### **8.2.5 Patient Global Impression of Change**

The PGI-C is a self-report tool to reflect a participant's belief about the efficacy of treatment. The PGI-C is a 7-point scale depicting a participant's rating of overall improvement. Participants rate their change from '1 – Very much improved' through to '7 – Very much worse'.

### **8.2.6 Patient Global Impression of Severity**

The PGI-S is a self-report tool to measure disease severity. The PGI-S is a 5-point scale, ranging from '1 – None', through to '5 – Very severe'.

### **8.2.7 Warwick-Edinburgh Mental Wellbeing Scale**

The WEMWBS is a scale of 14 positively worded items for assessing a population's mental wellbeing. The items cover both physiological functioning aspects of mental wellbeing (including: optimism, autonomy, agency, curiosity, clarity of thought and positive relationships) and positive affect (feelings, including: confidence, feeling relaxed, cheerful, having the energy to spare). The scale has 5 response categories, summed to provide a single score.

### **8.2.8 Post-Traumatic Growth Inventory**

The Post-Traumatic Growth Inventory measures the extent to which survivors of traumatic events perceive personal benefits, including changes in perceptions of self, relationships with others and philosophy of life, accruing from their attempts to cope with trauma and its aftermath. This 21-item scale includes factors of: new possibilities, relating to others, personal strength, spiritual change and appreciation of life.

### **8.2.9 Beck Depression Inventory-II**

The BDI-II is a 21-item self-report measure assessing depressive symptoms and their severity. Items include hopelessness and irritability, cognitions such as guilt or feelings of being punished, as well as physical symptoms such as fatigue and weight loss. Each item is rated on a 4-point scale, from 0 to 3. Items are summed to create a total score, with higher scores indicating higher levels of depression.

### 8.3 Sleep Quality Assessments

#### 8.3.1 Pittsburgh Sleep Quality Index

The PSQI is a measure of self-reported sleep quality and sleep disturbance. The PSQI contains 19 self-rated questions, which are combined to form 7 ‘component’ scores, each of which has a range of 0 to 3 points. The 7 components of the PSQI are: subjective sleep quality, sleep latency, sleep duration, habitual sleep efficiency, sleep disturbances, use of sleeping medications and daytime dysfunction. The sleep component scores are summed to yield a total score ranging from 0 to 21, with a higher total score indicating worse sleep quality.

[REDACTED]

#### 8.4.3 Blinding Integrity Questionnaire (Part B only)

The BIQ is a visual analogue scale that will be used to ascertain the degree of blinding; participants will be asked to circle a number from 0 (Strongly believe they received Placebo) to 10 (Strongly believe they received active drug) indicating which treatment they believed they were administered during the dose sessions.

The BIQ is administered during Part B only.

## **9 STATISTICS AND DATA ANALYSIS**

### **9.1 Randomization and Participant Allocation**

After informed consent is obtained, participants will be allocated a unique study number.

Only participants who comply with all the inclusion criteria, and none of the exclusion criteria will be randomized/enrolled onto the study. For Part A eligible participants will be enrolled into the open-label study.

For Part B, a randomization scheme will be produced by an unblinded Statistician in SAS 9.4 or higher. The participants will be randomized 1:1 in block sizes of 4 (2 treatments, 2 placebo) to the appropriate treatment (methylone or placebo) using an electronic Randomization and Trial Supply Management.

The participants in Part B will be assigned a randomization number in the order of randomization.

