## Overall Design

### **Brief Summary:**

This is a two-part study to assess methylone for the management of the symptoms of PTSD. Part A is an open-label, non-controlled assessment in approximately 15 evaluable participants with PTSD to assess early safety and efficacy and to confirm procedures included in the blinded portion (Part B) of the study. After completion of Part A, enrollment for Part B will begin in approximately 64 participants. Unless otherwise stated, Part B is identical to Part A with the exception of the inclusion of a placebo arm in Part B.

The open-label treatment in Part A is:

- Methylone 150 mg, with a booster administration of 100 mg administered 90 ( $\pm$ 10) minutes after the initial administration, during each dose session.

Part B is a randomized, double-blind, parallel-group, placebo-controlled assessment of methylone for the management of the symptoms of PTSD. This multi-center study will be conducted in up to 25 sites globally. Planned enrollment includes approximately 79 evaluable participants (approximately 15 in Part A and approximately 64 in Part B). There are 4 planned dose sessions for each participant. Participants in Part B will be randomized 1:1 to the two study treatment arms and will receive the randomized treatment at each of the weekly dose sessions for the duration of the study.

The two blinded study treatment arms in Part B are:

- Methylone 150 mg, with a booster administration of 100 mg administered 90 ( $\pm$ 10) minutes after the initial administration, during each dose session.
- Matched placebo at each timepoint (initial + booster) during each dose session.

For each participant in Parts A and B, the study will consist of:

- **Screening Period (Day -28 to Baseline):** Informed consent, eligibility assessment, and enrollment of eligible participants.
- **Baseline/Preparatory Session (Day -4 to Day -1):** Baseline assessments, confirmation of eligibility, and a preparatory psychoeducation session leading to enrollment confirmation.

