## Subjective Effects

Subjective effects of methylone on VAS subscales related to euphoria (stimulated, high, good effects, liking, feeling close to others), ARCI MBG subscale (euphoria), and the VESSPA SOC (pleasure and sociability) subscale, displayed dose-dependent increases in effects with higher doses. All methylone doses  $\geq 100$  mg were significantly different from placebo.

Changes in subjective effects measured using VAS and questionnaires were comparable between methylone and MDMA. The magnitude of the peak effects was similar between active drug treatments, however, methylone typically reached maximal response earlier (0.5 h vs 0.75 h) and resolved more quickly compared to MDMA (2.5-3 h vs 4 h). Changes in VAS were mainly related to stimulation and well-being, altered perception, and empathy.

Methylone was well tolerated, with no serious adverse events at doses ranging from 50 mg to 200 mg. A total of 3 subjects (21.4%) treated with methylone experienced a total of 5 treatment-emergent adverse events (TEAE). No TEAE term occurred in more than 1 subject. None of the TEAEs were considered to be related to methylone administration.

Dose-dependent increases in blood pressure and heart rate occurred after treatment with methylone. The maximum mean increase in systolic blood pressure was 25.2 mmHg at 0.75 h following administration of 200 mg methylone. Blood pressure increases were transient and returned to baseline values within approximately 3 hours at all doses. Temperature was relatively unchanged following methylone administration.

Overall, both methylone and MDMA administration resulted in significant physiological, subjective, and psychomotor effects compared to placebo. However, these effects occurred earlier and dissipated more quickly following methylone administration compared to MDMA administration. These results indicate that the pharmacological effects of methylone and MDMA occur before maximal plasma concentrations.

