Study Visit	Visit Timing	Brief Description of Events
Dose Session 1 (Visit 3 – Within 4 days of Baseline/ Preparatory Session	Day 1 – Predose	
Prior to enrollment (Part A) or randomization (Part B), an eligibility criteria review, a negative urine pregnancy test (WOCBP only), and urine drug screen will be required. Once confirmed that the participant meets all criteria, they will be enrolled (Part A) or randomized (Part B) onto the study. Predose assessments will then be performed (including vital signs, temperature, 12-lead ECGs, and C-SSRS).
 
Participants should have fasted (water only) for at least 2 hours prior to dosing and for at least 2 hours after the booster dose.
 
(Methyl) xanthine- and caffeine-containing products should be avoided for 2 hours predose until at least 8 hours after the initial dose.

	Day 1 – Dose Session 1 (~8 hours)	
Recording begins immediately prior to dosing.
 
Following dosing, adverse event monitoring begins.
 
The open-label treatment for Part A is:
 
 
Methylone 150 mg, with a booster administration of 100 mg administered 90 (±10) minutes later.
 
 
The two blinded study treatment arms for Part B are:
 
 
Methylone 150 mg, with a booster administration of 100 mg administered 90 (±10) minutes later.
 
Matched placebo (initial and booster).
 
 
Safety will be assessed at the following timepoints during the dose session:
 
 
BP and HR will be recorded 10 minutes predose and at 30-minute intervals (±15 minutes) post-administration until the end of the dose session 
 
In addition, BP and HR will be recorded within 15 minutes (+5 minutes) prior to administration of the booster dose (equivalent of 90-minute timepoint)
 
 
 
Temperature will be recorded predose and at 60-minute intervals (±15 minutes) post-initial dose-administration, until end of the dose session
 
12-lead ECG will be performed predose and at the end of the dosing session
 

	Day 1 – Discharge	
Prior to discharge, the dosing session monitor will encourage the participant to reflect on their experience.

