- During the early stages of the dose session, while the acute effects of methylone are active, the dosing session monitor will provide reactive support and engaged listening. The dosing session monitor will provide guidance if the participant falls into a negative pattern.
- At the end of each dose session, the dosing session monitor will encourage the participant to reflect on their experience and on any strong emotions or thoughts they might have encountered.

On Days 29, 36 and 43, post-dosing Reflection Sessions will be performed; the dosing session monitor will help the participant integrate their experiences over the four weeks of treatment, and to draw-out (if necessary) particular aspects of the experience. The dosing session monitor will assess and discuss the participant's symptoms, medical condition and psychological status/well-being following the treatment period.

Each dosing session should be recorded. The recordings will be reviewed to ensure the dosing session monitor is adhering to training and to facilitate training of future dosing session monitors.

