### **5.6.5 Management of Cardiovascular Events**

Elevations in blood pressure and heart rate are to be anticipated.

The risk of such elevations will be minimized by the inclusion/exclusion criteria and frequent monitoring of blood pressure and heart rate during each dose session.

Blood pressure and heart rate will be closely monitored with readings recorded at least every 30 minutes during the dose session. The study team will attend to clinical signs and symptoms of potential rare complications of the cardiovascular effects of methylone, such as stroke or acute myocardial infarction, during dose sessions. Any symptoms such as chest pain, shortness of breath, neurological deficit or confusion, or other potential indicators of end organ effects, will prompt additional vital sign measurements, and intervention if appropriate, and the participant will not receive any further doses of IMP and will be followed until resolution.

If a participant experiences ischemic type chest pain, whether or not it is associated with hypertensive crisis, they will be given 0.4 mg of sublingual nitroglycerin every 5 minutes as needed for chest pain pending transport to a hospital, and the Site Investigator will be promptly notified.

Further evaluation and management will be determined by the appropriate trained healthcare providers.

Participants experiencing a cardiovascular event associated with dosing that requires an intervention will not receive further dosing.

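### Protocol 9.1 prints one fixed block size of 4 and numbers participants in sequence without saying whether blocks are central or by site, so concealment of later assignments depends on a fact the plan does not give

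*Protocol*

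**What the plan says.** Protocol 9.1 fixes the allocation rule for Part B: "The participants will be randomized 1:1 in block sizes of 4 (2 treatments, 2 placebo) to the appropriate treatment". Assignment is made "using an electronic Randomization and Trial Supply Management" system, from a list produced by an unblinded statistician. The section adds: "The participants in Part B will be assigned a randomization number in the order of randomization". It names no other block length, no stratification factor and no blocking by site, and the SAP adds nothing on randomization beyond the 1:1 ratio. The Synopsis gives the spread of recruitment: "This multi-center study will be conducted in up to 25 sites globally".

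Randomization takes place on Day 1, after the eligibility review and before dosing (Protocol 4.2): "Once confirmed that the participant meets all criteria, they will be enrolled (Part A) or randomized (Part B) onto the study".

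On whether the arm can be recognised, Protocol 5.6.5 says "Elevations in blood pressure and heart rate are to be anticipated", and Protocol 2.4.2 reports that in healthy volunteers "both methylone and MDMA administration resulted in significant physiological, subjective, and psychomotor effects compared to placebo". A lead monitor is in the room for at least 8 hours at each of four sessions (5.3.1), and blood pressure and heart rate are read every 30 minutes (4.2).

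The safeguards are a securely held list (5.8), central raters who work remotely and do not see dose sessions (8), and dosing session monitors kept out of other research activities (5.3.1).

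**The concern.** Secure storage protects a list only if its contents cannot be rebuilt from what people already know. A short block of known length and composition can be rebuilt in part once its earlier arms are known. On a single list, a visible sequential number also shows the position in the block (the number modulo 4). Here the earlier arms may often be readable from the session itself.

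Foreknowledge has some room to act, because entry is decided before randomization and is not wholly mechanical. Exclusion criterion 12 relies on the clinical judgement of study personnel and covers inability to establish rapport with the monitor. The preparatory session, which covers goals and expectations, also precedes randomization. At stake are who is entered next and what that person is led to expect. The Blinding Integrity Questionnaire (8.4.3) asks participants only, so prediction by staff would go unmeasured.

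**Working it through.** **Inputs.** Block of 4 with 2 per arm (Protocol 9.1); up to 25 sites (Synopsis); about 64 participants in Part B (9.2). The plan gives no predictability figure to reproduce. Its 64 does reproduce: 27 evaluable per group / 0.85 = 31.8, so 32 per group. That number does not depend on the block size.

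**Step 1: observer who knows every earlier arm in the block without error.** There are 6 equally likely orderings of a 2:2 block.

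| Position | Certain | Best guess correct |
|---|---|---|
| 1 | 0 | 1/2 |
| 2 | 0 | 2/3 |
| 3 | 1/3 (first two alike) | 1/3 × 1 + 2/3 × 1/2 = 2/3 |
| 4 | 1 | 1 |

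Certain: (0 + 0 + 1/3 + 1)/4 = 33.3%, or 64/3, about 21 of 64. Guessed: (1/2 + 2/3 + 2/3 + 1)/4 = 70.8%. This is a ceiling.

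**Step 2: imperfect reading of earlier arms.** The documents give no accuracy, so it is assumed. If each earlier arm is read correctly with probability 0.80, 0.90 or 0.95, the guess rate is 60.1%, 64.9% or 67.7%.

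**Step 3: blocks within site.** Assume 64 participants fall evenly at random over the sites, and each site reads its own earlier arms correctly. With 25 sites the mean is 64/25 = 2.56 per site, so many blocks never reach position 4. Averaging the table over the positions reached gives about 16% certain and 63% guessed. With 10 sites it is about 27% and 68%.

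**Step 4: one central list, a site sees only its own participants.** Assume 25 equal sites and that the site knows its position in the block. At position i, the number m of earlier block members at the same site is Binomial(i − 1, 1/25), and the guess rate is 1/2, 2/3, 2/3 or 1 for m = 0, 1, 2 or 3. By position this gives 0.500, 0.507, 0.513 and 0.519, mean 51.0%, with about 0.05% certain. Fewer sites raise it: 52.4% guessed with 10, 54.4% with 5, 59.8% with 2.

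**Step 5: after the change, for the Step 1 observer.** Blocks of 4 and 6 are drawn with equal probability, and the observer knows the possible sizes but not which is in use. Simulated 64-participant lists, with the observer updating after each arm, give about 5.6% certain (0.056 × 64, about 4 participants) and 69.1% guessed.

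**Step 6: balance.** The largest imbalance on one list, wherever enrolment stops, is half the longest block: 4/2 = 2 now, 6/2 = 3 with mixed lengths.

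**The case against.** The strongest reply is that 9.1, with no stratification and numbers issued in order of randomization, reads most naturally as one central list. A site is then close to guessing by chance. The headline 33.3% and 70.8% need an observer the documents do not describe. This part stands, and the risk has to be stated conditionally.

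A reader might infer that reviewers of recordings are that observer. Protocol 5.3.1 says only: "The recordings will be reviewed to ensure the dosing session monitor is adhering to training and to facilitate training of future dosing session monitors". It does not say that one person sees every session, in order, before the next randomization, or that reviewers influence entry.

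The entry decision is also more constrained than it may look. Section 6 allows no exceptions to the criteria, severity is scored by central raters, and the monitor has no other research role. This narrows the opening without closing it, because exclusion criterion 12 keeps judgement and refers to rapport with that monitor.

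The physiological evidence needs its caveat too. The 25.2 mmHg maximum mean systolic rise in Protocol 2.4.2 followed a single 200 mg dose in healthy volunteers, whereas this trial gives 150 mg and then 100 mg. Frequent recognition of the arm is a reasonable inference, not a reported fact.

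Finally, small blocks do have a benefit, which is balance, and varying the lengths hardly lowers the all-seeing observer's guess rate. Both are true. The gain is in certain knowledge, the strongest basis for selective entry.

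**Conclusion.** The concern holds in conditional form. A single block length and its composition are disclosed, numbers run in sequence, and the blocking level is not stated. Depending on that missing fact, predictability runs from about 51% guessed (central list, 25 equal sites, own participants only) through about 63% guessed and 16% certain (site-level blocks, 25 even sites) to a ceiling of 70.8% guessed and 33.3% certain (all earlier arms known). These figures assume error-free reading of the earlier arms that the observer sees, and even recruitment where sites enter. Less accurate reading lowers them; recruitment concentrated at a few sites raises them.

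This is a low-to-moderate risk to allocation concealment at entry. Three stronger readings are not supported: that sites can in general work out the next assignment, that selection bias has occurred, or that the primary ratings are compromised by the block size. The first needs site-level blocks, concentrated recruitment or a cross-site observer, and the documents establish none of these. Nothing in them bears on the second. Against the third, CAPS-5 is rated remotely by people who do not see dosing.

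**What to change.** For allocations not yet used:

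- Have the unblinded statistician generate the list with randomly varying block lengths, for example 4 and 6.
- Keep the lengths and the blocking level only in a restricted randomization specification.
- Remove the block size from Protocol 9.1 at the next amendment.
- Do not show sequential randomization numbers to sites.

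The cost is an update to the unused part of the list in the randomization system and one amended phrase, which needs written IRB/EC approval (Protocol 12.2). The statistical price is the rise in maximum imbalance from 2 to 3 on one central list. If blocks run by site, imbalances add across sites. The sample size is unaffected.

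SAP 3.1 says Part B enrolment has begun, and the documents do not show how many allocations remain. If none do, report in the clinical study report whether blocks were central or by site, and who could see the sequence and the dose sessions.
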